BIOTRONIK may pool data from other prospective studies to supplement the Plexa Registry population to achieve the sample size of 1271 subjects needed for the primary endpoint analysis. The data collection would need to be sufficiently similar to the Plexa Registry data collection to allow pooling of the data. If data from other studies are used, the data will come from subjects who have a US market released BIOTRONIK ICD or CRT-D pulse generator and a successfully implanted Plexa lead.

Figure 5: Registry Design Flowchart

[figure not shown]
[figure not shown]

Figure 6: Visit Schedule

* In-office visit may be performed at 24, 30, or 36 Month interval

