2.3 SAMPLE-SIZE ANALYSIS

The investigation is designed to limit the number of subjects involved while still exposing the device to a sufficiently large patient population in order to ensure a representative and statistically meaningful sample.

The estimated sample size required to evaluate primary endpoint 1 is based on a superiority comparison of the overall Plexa lead AE-free rate to 92.5% at 5 years. The sample size for primary safety endpoint 1 was calculated based on the following assumptions:

Assumptions for primary safety endpoint 1

- Registry Design: nonrandomized registry
- Test basis: exact binomial test
- Type I error (alpha): 0.025 (one-sided for superiority)
- Statistical power: 80%
- Estimated AE-Free Rate at 5 years: 95.0% for Plexa leads
- Performance goal for AE-Free Rate at 5 years: 92.5%

For primary safety endpoint 1, a total of 750 evaluable Plexa leads would be required to demonstrate superiority to an AE-free rate of 92.5%. Assuming a 10% loss to follow-up rate per year over 5 years of follow-up (average of 8.2% of original population per year), a total of 1271 ($= 750 / 0.9^5$) subjects with an ICD lead would be required to be enrolled to evaluate primary safety endpoint 1.

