2.4.2 Trend Analyses

The primary safety endpoint is evaluated at 5 years post-implant against pre-specified performance levels (92.5% for overall freedom from Plexa lead-rated AEs). To monitor the ongoing incidence of any potential AEs against the accumulating follow-up exposure post-implant, Kaplan-Meier survival curves may be prepared at the reporting intervals for Primary Endpoint 1. Root causes for any failures, regardless of the incidence rates, may be investigated.

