2.4.4 Poolability Analysis

The distribution in AE-free rates across centers will be examined. The significance of differences in rates between centers will be initially tested using a Kruskal-Wallis test statistic, with an associated p-value of 0.15 or less considered evidence of center differences.

Additionally, a Cochran-Mantel-Haenszel test with continuity adjustment will be used to assess the poolability of data collected across the different centers. If evidence is found of center differences, then the reasons for the differences will be explored using Cox and logistic regression methods to determine if any baseline subject risk factors are explanatory.

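### The sponsor may add subjects from unnamed studies to the primary test with no outcome-blind trigger, across-study comparison or required registry-only result

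*Combined protocol and SAP*

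**What the plan says.** Section 2 (Registry Design): "BIOTRONIK may pool data from other prospective studies to supplement the Plexa Registry population to achieve the sample size of 1271 subjects". The section adds that this number is needed for the primary endpoint analysis, so pooled subjects enter the confirmatory test. It sets two conditions: data collection must be similar enough to permit pooling, and subjects must have a marketed generator from the sponsor and an implanted Plexa lead. It gives no list of studies, no trigger, no decision date and no criterion for similarity.

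Section 2.4.2 (Trend Analyses): "Kaplan-Meier survival curves may be prepared at the reporting intervals for Primary Endpoint 1". The registry is single-arm, Section 4.3 has the sponsor review the registry data, and Section 11.4 requires progress reports at least yearly.

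Section 2.4.4 (Poolability Analysis) tests whether event-free rates differ between centers, and a second test is to "assess the poolability of data collected across the different centers". Source study is not a factor. No section calls for the primary result in registry subjects alone.

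Section 2.3 sizes the study for a binomial test, done exactly, of the five-year event-free rate against a goal of 92.5%. The design value is "Estimated AE-Free Rate at 5 years: 95.0% for Plexa leads", with a one-sided alpha of 0.025 and power of 80%. This gives 750 evaluable leads and 1271 enrolled.

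**The concern.** A one-sample test against a fixed goal keeps its error rate only if the set of subjects analysed does not depend on the results. Here the sponsor may decide whether, when and from where to add subjects, and may have seen primary endpoint curves first. If pooling is used only when the registry alone would miss the goal, the trial has two chances of success, each tested at 2.5%.

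A second problem needs no selection. A source study that detects or classifies events less completely raises the pooled event-free rate. The planned analyses would not show this directly, because they neither compare studies nor report the registry alone.

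At stake is the claim that the five-year event-free rate exceeds 92.5%.

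**Working it through.** **Inputs from Section 2.3.** Null rate 92.5%, expected rate 95.0%, one-sided alpha 0.025, exact binomial test, 750 evaluable, attrition 10% per year.

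**Assumptions not in the documents.** How the 750 evaluable subjects divide between registry and source study; a single source study; and, in step 4, a 94.5% event-free rate in that study.

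**1. The plan's own figures.** Success requires the smallest r with P(X ≥ r | n = 750, p = 0.925) ≤ 0.025. This gives r = 708, that is, at most 42 subjects with an event.
- Type I error: P(X ≥ 708 | 0.925) = 0.0247.
- Power: P(X ≥ 708 | 0.95) = 0.801.
- Enrollment: 750 / 0.9^5 = 750 / 0.59049 = 1270.1, rounded up to 1271.

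The sample size is reproduced.

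**2. Pooling fixed without sight of outcomes, equal rates.** The pooled count is still binomial with n = 750 and p = 0.925, so the error stays at 0.0247.

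**3. Success from either the registry-only or the pooled test.** Let n1 be the registry evaluable count, n2 = 750 − n1, and r1 the exact critical value at n1. With p = 0.925 throughout:

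P(success) = P(X1 ≥ r1) + Σ over x < r1 of P(X1 = x) · P(X2 ≥ 708 − x)

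| Registry + source | r1 | Registry-only error | Either test succeeds |
|---|---|---|---|
| 650 + 100 | 615 | 0.0205 | 0.0307 |
| 600 + 150 | 568 | 0.0223 | 0.0336 |
| 500 + 250 | 475 | 0.0167 | 0.0327 |
| 400 + 350 | 381 | 0.0183 | 0.0359 |

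At the planned retention of 0.59049, the two ends of this range correspond to 650 / 0.59049 ≈ 1101 and 400 / 0.59049 ≈ 677 enrolled in the registry.

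**4. No selection, but a source study with narrower event capture.** The registry rate is 92.5% and the source study records 94.5%.
- 20% of the pool (600 + 150): mean rate 0.8 × 0.925 + 0.2 × 0.945 = 0.929. P(at least 708 of 750) = 0.059.
- 40% of the pool (450 + 300): mean rate 0.6 × 0.925 + 0.4 × 0.945 = 0.933. P(at least 708 of 750) = 0.127.

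**The case against.** **The cap limits the exposure.** Pooling is tied to reaching 1271, which Section 2.3 gives as the number to enroll. A registry that enrolls 1271 itself has no room to pool. This stands: the inflation in step 3 arises only under a shortfall, and pooling may never be used. The curves in Section 2.4.2 are also optional, although the sponsor's access to event data does not depend on them.

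**Registry rules may already cover pooled subjects.** A reader might infer that nothing makes pooled subjects meet this registry's rules. The text does not support that. Section 2.4 limits the primary analysis population to consented subjects who met the enrollment criteria, and Section 3.1.3 includes the 30-day window. Sections 6.2 and 9.2 send every protocol-defined event in the endpoint analysis to the Clinical Events Committee, and Section 9.3.1 defines which events count. None of these exempts pooled subjects. They do not mention them either, and Section 6.2 also describes the committee's work as covering events during the registry. What remains is a need for clarification.

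**Center tests might pick up a study effect.** If pooled sites enter Section 2.4.4 as centers, a difference could partly show at the 0.15 threshold. With up to 75 registry sites and few events, however, a test across centers is poorly aimed at a difference between studies. The only stated consequence is to explore the reasons.

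**Earlier registries as evidence of differing capture.** A reader might point to the 180-day dislodgement cut-off in GALAXY and the 30-day one in Protego. Those registries studied other leads, whereas Section 2 admits only Plexa subjects. Protego's dislodgement window also matches the one in Section 9.3.1.

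**Several source studies.** One can obtain 4.0% (600+75+75) or 3.9% (500+125+125) with two sources, but only by allowing success from any of four data sets. These include pools of 675 and 625 evaluable subjects that do not reach 750. With only the registry alone and the full pool allowed, the same splits give about 0.034 and 0.033.

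**Conclusion.** The concern holds in a limited form. The plan allows outside subjects into the confirmatory test without an outcome-blind trigger or pre-named sources, compares centers but not studies, and requires no registry-only result.

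Under a shortfall with a results-dependent choice, the one-sided error moves from 0.0247 to about 0.031 to 0.036. That range rests on the assumed splits and one source study. The capture figures of 5.9% and 12.7% are a separate matter: they rest on an assumed 94.5% source rate, involve no selection, and should not be read as the effect of results-driven pooling. They are also the larger risk, because an outcome-blind decision would not remove them.

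The documents do not show that the sponsor intends to choose on results, and the sample size is not in error. This should be corrected before any pooling decision; it does not invalidate the design.

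**What to change.** - In Section 2, base the decision to pool on enrollment counts alone. Name the source studies and date that choice before any adverse event summary is reviewed.
- State that the enrollment criteria (Sections 2.4 and 3.1.3), committee adjudication (Sections 6.2 and 9.2) and the event definitions in Section 9.3.1 apply to pooled subjects.
- Add source study as a factor in Section 2.4.4.
- Always report the registry-only result beside the pooled one.

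No alpha adjustment is needed if the pooling decision is blind to outcomes and the rates are equal. The cost is protocol wording, some committee review of pooled events, and the loss of freedom to decide late.

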Title:	Plexa Registry
Design:	Prospective, single-arm, non-randomized, multi-center registry
Purpose:	To confirm the long-term safety and reliability of BIOTRONIK’s Plexa lead, as used in conjunction with a US market released BIOTRONIK implantable cardioverter defibrillator (ICD) or cardiac resynchronization therapy defibrillator (CRT-D) pulse generator. The evaluation of safety will be based on the analysis of Plexa lead-related adverse events. The Plexa Registry will provide data to permit characterization of Plexa lead failures contributing to loss of bradycardia pacing or shock therapy. Additionally, acute and chronic Plexa lead parameters will be evaluated.
Subject Population:	Subjects who are indicated for an ICD or a CRT-D. Subjects must be successfully implanted with a compatible US market released BIOTRONIK ICD or CRT-D. Subjects can be enrolled no more than 30 days after successful implantation of the Plexa system.
Enrollment:	This registry is designed to follow 1271 subjects implanted with the Plexa system through 5 years post-implant.
Clinical Sites:	Up to 75 US sites.
Primary Endpoint:	Overall incidence of adverse events (AEs) related to the Plexa lead
Secondary Endpoints:	
 1. Incidence of each individual type of AE that contributes to Primary Endpoint 1 2. Pacing threshold, sensing, and impedance measurements for the Plexa lead through 5 years post-implant 3. Shock impedance for the Plexa lead through 5 years post-implant 4. AE rates for AEs excluded from primary safety endpoint 1, through 5 years post-implant
Clinical Events Committee Chair:	[name] State Health Center [name] Hungary
Sponsor:	BIOTRONIK, Inc. Clinical Studies Department [name] [name]

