2.4.3 Missing Data

All possible steps will be taken to minimize missing data in the registry. This includes but is not limited to monitoring of registry electronic case report forms (eCRFs) for completeness and supporting efforts to track and maintain contact with registry subjects during the follow-up period.

The reasons for any missing data in the registry should be documented. BIOTRONIK Home Monitoring[®] can provide daily automatic sensing values, pacing thresholds, shock impedance, and pacing impedance, depending on the device programming. When available, missing data will be imputed with BIOTRONIK Home Monitoring[®] values obtained from the day of a completed follow-up, target date of a missed follow-up, or the next closest day in the visit window.

For evaluation of primary endpoint1, only subjects who achieve 5 years of follow-up or have experienced an adverse event prior to 5 years will be included in the final evaluation of the associated hypotheses. The secondary endpoints 1 and 4 of other AEs at 5 years will be analyzed in a similar manner. There will be no imputation for these missing adverse event outcomes.

For purposes of the final report Kaplan-Meier survival analyses, all AE data on enrolled non-replaced subjects will be included with follow-up times censored at the time of exit or last completed study visit representing the time of the last known AE status.

Secondary endpoints 2 and 3, which include pacing thresholds, sensing, pacing impedance, and shock impedance measurements will be summarized by scheduled visit through the 5 years of registry follow-up

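### The pooling rule in Section 2 targets 1271 subjects and sets no follow-up length, whereas the primary test needs 750 subjects evaluable at 5 years

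*Combined protocol and SAP*

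**What the plan says.** Section 2 (Registry Design) permits pooling from other prospective studies "to supplement the Plexa Registry population to achieve the sample size of 1271 subjects needed for the primary endpoint analysis". It sets three conditions: data collection similar enough to the registry's to be combined, a market-released generator from the sponsor, and a successfully implanted Plexa lead. It does not say how long pooled subjects must be followed, or that they must be evaluable at 5 years.

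Section 2.3 gives the number that carries the power: "a total of 750 evaluable Plexa leads would be required to demonstrate superiority to an AE-free rate of 92.5" percent. It then obtains 1271 by dividing 750 by 0.9^5, to allow for 10% attrition per year over 5 years. Section 2.3.2 again names 750 as the number required for primary endpoint 1.

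On who enters the test, Section 2.4.3 says that "only subjects who achieve 5 years of follow-up or have experienced an adverse event prior to 5 years will be included", and that missing AE outcomes are not imputed. Section 2.4 defines the primary analysis population in the same way.

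**The concern.** The two numbers do different jobs. The 750 is a count of subjects with a usable 5-year outcome. The 1271 is the number to enroll so that 750 remain, if every subject is intended to be followed for 5 years and 10% leave each year. Section 2 applies the enrollment number to pooled subjects, for whom 5-year follow-up is not required.

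An AE-free subject from a study that ends before 5 years takes a place in the 1271 but can never enter the primary test. A subject from the same study who has a primary endpoint AE does enter. Such a study therefore contributes events and no AE-free subjects. Two things follow: fewer evaluable subjects than planned, and an AE-free rate that is biased downward. The sponsor could follow the text, report the sample size as reached, and test with less than the stated 80% power.

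**Working it through.** **Inputs from Section 2.3.** "Test basis: exact binomial test"; one-sided alpha 0.025; power 80%; "Estimated AE-Free Rate at 5 years: 95.0% for Plexa leads"; performance goal 92.5%; attrition 10% per year for 5 years.

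**Step 1: reproduce the plan's figures.** For n evaluable subjects, take the smallest r with P(X ≥ r | n, 0.925) ≤ 0.025. Power is then P(X ≥ r | n, 0.95). At n = 750, r = 708, so at most 42 subjects may have an AE; the exact alpha is 0.0247 and power is 80.1%. No smaller n reaches 80%. Inflation: 750/0.9^5 = 750/0.59049 = 1270.1, rounded up to 1271. Both stated figures reproduce.

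**Step 2: slack at planned attrition.** 1271 × 0.59049 = 750.5. There is essentially no room for a subject who cannot become evaluable.

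**Step 3: replace k of the 1271 by AE-free subjects from a study shorter than 5 years.** The documents give no value for k, so 200, 300 and 400 are assumptions. Evaluable registry subjects = (1271 − k) × 0.59049. Exact power is saw-toothed in n (80.1% at 750, 79.9% at 751, 75.6% at 749), so the fair comparison averages it over all n within 10 of each value.

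| k (assumed) | Evaluable registry subjects | Averaged power |
|---|---|---|
| 0 | 1271 × 0.59049 = 750 | 78% |
| 200 | 1071 × 0.59049 = 632 | 69% |
| 300 | 971 × 0.59049 = 573 | 65% |
| 400 | 871 × 0.59049 = 514 | 60% |

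These figures reflect the smaller n only.

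**Step 4: sensitivity to attrition.** The number of non-evaluable pooled subjects that 1271 can absorb while leaving 750 is 1271 − 750/(1 − a)^5, for yearly attrition a (8% and 5% are assumed values).

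- a = 10%: 1271 − 1270.1, about 0
- a = 8%: 1271 − 750/0.6591 = 1271 − 1138, about 133
- a = 5%: 1271 − 750/0.7738 = 1271 − 970, about 301

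**Step 5: direction of the bias.** Assume a constant AE hazard of −ln(0.95)/5 = 0.01026 per year, an exit hazard of −ln(0.9) = 0.10536 per year, and a 2-year source study. The chance that a pooled subject enters with an AE is 0.01026/0.11562 × (1 − e^(−0.11562 × 2)) = 0.0183. With k = 200 that is about 3.7 added events and no AE-free subjects. If the 632.4 registry subjects are held at 95.0% AE-free, the expected rate becomes 0.95 × 632.4/(632.4 + 3.7) = 94.5%. This shows the direction and rough size under assumed inputs. It is not turned into a power figure, for the reason given under the objection.

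**The case against.** The strongest reply is that the intended meaning can be recovered. The registry's data collection runs to 60 months, so a short study might fail the similarity condition. Section 2.3.2 names 750 as the requirement and lets early exits be replaced while enrollment is ongoing. Section 2 gives no explicit rule for counting pooled subjects. That is a reasonable reading, but the text does not compel it. Registry subjects must be available for 5 years (Section 3.1.3), and no such condition is placed on pooled subjects.

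The reply is right that the harm is conditional. Pooling is optional, its size is not stated, and no short source study is identified. Section 2.3.1 calls 10% per year a maximum, although Section 2.3.2 calls it expected. At 5% per year, the cases k = 200 and k = 300 show no shortfall.

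A reader might also infer a much larger loss by adding the pooled subjects' events to the smaller n and attributing the whole fall in power to pooling. The documents do not support that. The rule in Section 2.4.3 applies equally to the registry's own early exits, who stay in with an AE and drop out without one. Under the Step 5 hazards, applying the rule to all 1271 subjects with no pooling already gives an expected AE-free rate of 93.5% and power of about 16%. Most of such a loss would come from the analysis-set rule, which is a separate matter.

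Nor does it follow that the enrollment statements in the synopsis and Section 2.2 are errors. They describe a design intention, and the 41% attrition is stated openly in Sections 2.3.1 and 4.4.

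**Conclusion.** The point holds as a conditional gap in the pooling rule. Section 2 describes 1271 as the number the primary analysis needs, while Sections 2.3, 2.3.2, 2.4 and 2.4.3 make it 750 evaluable subjects. Nothing in the pooling conditions prevents subjects who cannot reach 5 years from completing the count.

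Power from the smaller n alone falls by about 9, 13 or 18 percentage points (from 78% to 69%, 65% or 60%). This rests on the assumed pooling of 200, 300 or 400 such subjects, attrition at the planned 10% per year, and the plan's 95.0% AE-free rate. At lower attrition part or all of the loss disappears. The downward bias in the AE-free rate adds to it, but its size depends on a source study that the documents do not describe. The documents do not show that a shortfall will occur, only that the rule permits one. The wording should be settled before any decision to pool.

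**What to change.** In Section 2, replace the pooling target of 1271 with 750 subjects evaluable for primary endpoint 1 at 5 years, meaning AE-free through 5 years or with a primary endpoint AE before then. Add a condition that data are pooled into the primary test only from studies with planned follow-up of at least 60 months post-implant. Data from shorter studies may enter only the Kaplan-Meier analysis, censored at study end, in line with how Section 2.4.3 already treats early exits there.

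The cost is protocol wording. The downside is that fewer outside studies qualify for the primary test.

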2.1 REGISTRY ENDPOINTS

This registry includes the assessments of one primary safety endpoint related to the Plexa lead and several secondary endpoints that evaluate the safety and effectiveness of the Plexa system.

2.1.1 Primary Endpoint 1

The purpose of primary endpoint 1 is to evaluate the overall incidence of adverse events related to the Plexa lead (as defined in Section 9) from implant through 5 years. Assuming that the expected Plexa lead adverse event rate at 5 year post-implant (proportion of subjects with at least one AE in the timeframe from implant through 5 year post-implant) is 7.5% or less, then the primary safety endpoint will be evaluated in the following testable hypothesis in superiority format.

H_0 : The adverse event-free rate (AEFR) for subjects receiving the Plexa lead at 5 years post-implant is less than or equal to 92.5%

$$AEFR \leq 92.5\%$$

H_a : The adverse event-free rate (AEFR) for subjects receiving the Plexa lead at 5 year post-implant is greater than 92.5%

$$AEFR > 92.5\%$$

If the two-sided, 95% lower confidence bound is greater than 92.5%, then the null hypothesis will be rejected.

2.1.2 Secondary Endpoints

There are no formal tests of hypotheses associated with secondary endpoints 1-4.

1. Incidence of each individual type of AE that contributes to Primary Endpoint 1
2. Pacing threshold, sensing and impedance measurements for the Plexa lead through 5 years post-implant
3. Shock impedance for the Plexa lead through 5 years post-implant

4. Adverse event rates for protocol defined, Clinical Events Committee (CEC) adjudicated AEs excluded from primary safety endpoint 1, through 5 years post-implant

2.1.3 Additional Data of Interest

Additional information may be collected to characterize the registry population, implanted system, and progress of the registry. When available, the collected information may include baseline demographics, medical history, implanted system, system revisions, Plexa lead extractions, returned product analysis, and compliance. Specifically, data of interest may include:

- Baseline demographics, such as date of birth, gender, height, weight, and New York Heart Association (NYHA) class (if available)
- Medical history, including indication for device
- Implanted device data from initial implant and / or revisions, including implant dates and manufacturers for all implanted pulse generator and leads. Additionally, models and serial numbers will be collected for BIOTRONIK pulse generator and leads.
- Implant procedure data (collected retrospectively at enrollment)
- Revision procedure data (may be collected retrospectively)
- Plexa DX lead atrial dipole sensing measurement
- Results from returned product analysis
- Compliance to protocol requirements and registry visit schedule

